- 06 Loss of source documents/samples/source media
- 07 Ineligible subject enrolled
- 08 Subject in more than one simultaneous interventional trial
- 09 Informed Consent/HIPAA documentation completed incorrectly
- 10 Informed Consent/HIPAA documentation is incomplete
- 11 Informed Consent/HIPAA not obtained prior to study procedures
- 12 Used incorrect informed consent/HIPAA version
- 13 Required study procedure not performed per protocol
- 14 Study activities performed by inappropriate personnel
- 15 Study intervention not administered per protocol
- 16 Subject noncompliance
- 17 Other (specify under Details of noncompliance)

MI #	SITE NO.	SUBJECT ID	ALPHA CODE	DATE FORM COMPLETED		
	  	   	   	 	 	   
				Month	Day	Year

FORM 19 – CONFIRMATION OF MYOCARDIAL INFARCTION BY LOCAL SITE

1. Date of study surgery (index CABG)
 Month Day Year
2. Date of myocardial infarction (MI)
 Month Day Year
3. Supporting documentation (universal definition of MI):

ECG Changes Development of new ST-T changes

All that apply

Development of new LBBB

Development of new pathologic Q-Waves

If any ECG changes marked above, **you must complete A, B, OR C below**

A. Peak Cardiac Troponin I

1. Peak Cardiac Troponin I (ng/mL): .

2. Reference Range (ng/mL): . to .

B. Peak Cardiac Troponin T

1. Peak Cardiac Troponin T (ng/mL): .

2. Reference Range (ng/mL): . to .

C. Peak CPK/MB Panel

1. Peak Total CPK (U/L):

2. Total CPK Reference Range (U/L): to

3. Peak CK-MB (ng/mL): .

4. CK-MB Reference Range (ng/mL): to .

5. Peak CK-MB Index (%): .

6. CK-MB Index Reference Range (%): . to .

Form 19 – Confirmation of Myocardial Infarction

MI #

SITE NO.

--	--	--

SUBJECT ID

--	--	--	--

ALPHA CODE

--	--	--	--

4. Other Supporting Documentation (check all that apply)

- Imaging evidence of loss of viable myocardium or new regional wall motion abnormality
- Symptoms of ischemia
- Angiographic documenting new graft or new coronary occlusion

S.I. Signature _____

Date _____

Form 20 – Classification of Myocardial Infarction

MI #	SITE NO.	SUBJECT ID	ALPHA CODE	DATE FORM COMPLETED
	  	   	  	    Month Day Year

FORM 20 – CONFIRMATION OF MYOCARDIAL INFARCTION BY CLINICAL EVENTS COMMITTEE

1. Clinical Events Committee Confirms Diagnosis of Myocardial Infarction: No Yes

If yes, proceed to question 2.

If no, STOP, sign form and submit to the Perry Point Coordinating Center.

2. Classification of myocardial infarction: (select one)

- Type 1 Spontaneous myocardial infarction
- Type 2 Myocardial infarction secondary to an ischemic imbalance
- Type 3 Myocardial infarction resulting in death when biomarker values are unavailable
- Type 4a Myocardial infarction related to percutaneous coronary intervention (PCI)
- Type 4b Myocardial infarction related to stent thrombosis
- Type 5 Myocardial infarction related to coronary artery bypass grafting (CABG)

3. Committee comments (if applicable): _____

Form Completed By: _____ Date _____

Signature of Chair, Clinical Events Committee / PRINTED NAME Date

Form 21 – Cause of Death

SITE NO.	SUBJECT ID	ALPHA CODE	DATE FORM COMPLETED																					

 	 	 	

				

 	 	 	 	

					

 	 	 	 	

					

 	 	

			

 	 	

			

 	 	 	 	

				
			Month	Day	Year																			

FORM 21 – CAUSE OF DEATH BY CLINICAL EVENTS COMMITTEE

1. Date of Death

--	--

 Month

--	--

 Day

--	--	--	--

 Year

Cause of Death

a. Specific cause of death (based on review of available medical chart data)

b. Primary cause of death was most likely

- Cardiac related
- Not cardiac related
- Unknown

c. Detailed information about primary cause of death by category

 Accident	 Cerebrovascular
 Suicide	 Pulmonary
 Infection	 Cancer
 Cardiovascular	 Other

Completed by _____ Date _____

VA COOPERATIVE STUDY #588

RANDOMIZED ENDO-VEIN GRAFT PROSPECTIVE – REGROUP TRIAL

Site Selection Process: Vein Harvester Qualification Policy

1. VA sites with active Cardiac Surgery Programs are contacted with introductory letter including executive summary and relevant manuscripts via email.
2. Interested sites provide high-level overview of the sites Cardiac Surgery Service eligibility criteria:
 - established EVH program >2years,
 - sufficient isolated CABG volume to enroll 2-3 subjects/month x3 years,
 - willingness to randomize to EVH vs. OVH,
 - at least one harvester experience includes > 100 EVH with conversion rate \leq 5%,
 - ability to competently provide care for OVH procedure.
3. All potential sites complete CSP #588 Form 15 for each individual harvester who is expected to perform the vein harvesting procedure as part of normal daily job duties during the course of study participation at the site. The forms are signed by the site Principle Investigator (site surgeon investigator) as verification.
4. Each completed form is submitted to and reviewed by the Study Chair's office.
5. A Subcommittee of the Executive Committee will review each site case by case to determine eligibility status and designate each site as one of the following:
 - A. Site with at least one harvester experienced in BOTH EVH and OVH confirmed by the site surgeon investigator => site confirmed as qualified for study participation and harvester assigned a code by CSPCC.
 - B. Site with at least one harvester experienced in EVH but NOT OVH confirmed by the site surgeon investigator => site confirmed as qualified for study participation only IF a designated harvester for OVH is identified, assigned a code by CSPCC, and MUST be immediately available, in addition to the EVH harvester, at time of randomization and harvesting (i.e. the site surgeon investigator).
 - I. Site with NO harvester experienced in EVH and/or incapable of providing OVH procedure=> site is INELIGIBLE for study participation at this time regardless of interest level or CABG volume.

Subcommittee Members: [name] [name], FETCS; [name], PA-C; [name], CRNP

CSP #588

RANDOMIZED ENDO-VEIN GRAFT PROSPECTIVE – REGROUP TRIAL

Version 1.2 Protocol

October 1, 2013

F-1

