the role of EVH on premature graft loss (Ouzunian 2010) which may be explained by variability of techniques and level of experience among centers. Desai and associates, in a prospective pilot study using Optical Coherence Tomography (OCT) imaging, noted that veins procured by novice harvesters had nearly 50% more discrete injuries than veins procured by experienced harvesters (Brown 2007). Rousou and colleagues recently reported that, compared to OVH, EVH adversely affects vein endothelial function (Rousou 2009). They used epifluorescence multiphoton microscopy (a technique that measures endothelial viability and functionality in real time with greater sensitivity than other methods) and demonstrated endothelial and smooth muscle cell damage in vein grafts with reduced endothelial cell viability, attenuated calcium mobilization, and nitric oxide production in the EVH group. Endothelial dysfunction enhances thrombogenicity and may lead to early thrombosis and accelerated SVG failure. Compromised endothelial integrity is the primary determinant in the interrelated pathogenesis of thrombosis, intimal hyperplasia and atherosclerosis within the SVG (Thatte 2001). Considering all the basic science and clinical arguments, together with increased risk of adverse events that inevitably follows graft failure, the goal of harvesting SVG with as near-perfect integrity of its intima layer as possible seems prudent until available evidence demonstrates otherwise.

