All participating vein harvesters must meet the minimum EVH/OVH volume criteria [at least 100 EVH cases with low conversion rates (<5%) as part of an EVH program established for more than two years] to be eligible to enroll subjects in this study. Unless an urgent medical condition exists, the subject's surgery will be scheduled to occur at the earliest possible date based on expert harvester availability and other center circumstances. The randomization procedure will occur after the participating expert harvester is assigned to the subject. Subjects will be randomized within the assigned participating harvesters to one of the two study harvesting technique arms (EVH or OVH).

Recognizing that the subject's assignment to a participating vein harvester will have already occurred, the study randomization to either EVH or OVH will be done by a telephone call to the Perry Point Cooperative Studies Program Coordinating Center (CSPCC). A block randomization scheme will be used to randomize subjects in two treatment groups. A random sequence of block sizes will be used to reduce the chances of guessing future allocations.

C. Subject Assessments

Baseline assessments will be collected prior to surgery and randomization including Body Mass Index, Ankle-Brachial Index and Venous Clinical Severity Scale. Intraoperative assessments will be collected during the CABG procedure, 24 and 48 hours postoperatively as well as assessments at the time of hospital discharge or 30 days post-surgery, whichever occurs first. Subjects will return for a six-week clinic visit to assess the condition of their leg incision and healing status. Any necessary medical care required will be administered per the Institution's standard practice.

Subjects will receive a phone call every three months for follow-up for events until subject termination. Subjects will complete QoL surveys again at one year either by telephone or mail. If the subject reports a major adverse cardiac event (e.g. MI, repeat revascularization) after discharge from the hospital, then records will be obtained for final adjudication. Ascertainment for death will include review of VA central databases.

Following is a list of assessments/study details that we plan on collecting:

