Post-operative Lab and Diagnostic Test Evaluation: Twelve-lead EKGs will be obtained on the first two post-op days as noted in the detailed data forms. This is a routine test, commonly performed as part of usual postoperative clinical care for CABG patients. In the event the 12-lead EKG indicates either new pathologic Q waves or a new Left Bundle Branch Block, cardiac biomarker levels (preferably cardiac Troponin) will be collected from the subject every eight hours until a downward trend is seen. The peak cardiac biomarker value and reference range (including the 99th percentile of the Upper Reference Limit- URL) will be collected on the postoperative data collection Form 6.

30-Day Operative Mortality Assessment: Subjects will be noted to have died in-hospital or discharged alive. For subjects discharged alive, their vital status will be reassessed at 30 days post-CABG.

30-Day Morbidity Assessment: The presence/absence of major post-operative complications that occurred prior to discharge or within 30 days of CABG will be recorded. Leg wound healing assessments and infection data will also be collected at discharge.

In-hospital Resource Use: Several in-hospital indicators including operating room time, extubation time (with reintubation times noted), SICU length of stay, pre-operative and postoperative length of stay, and total blood product use (both intraoperatively and post-operatively) will be measured.

See Schedule of Events below:

Table 2. Schedule of Events

FORM	SCREEN	BASELINE (pre op) Visit 00	INTRA OP Visit 00	POST OP Visit 00	DC- 30 DAY Visit 01	6 WK Visit 02	3 MO Visit 03	6 MO Visit 06	9 MO Visit 09	12 Mo Visit 12	... Every 3 Mo	45 MO Visit 45	49 MO Visit 49	AS NEEDED
00 – Screening Log	X													
01 – Screening and Randomization	X													
02 – Baseline Information		X												
03 – Seattle Angina Questionnaire		X				X				X				
04 – VR-12		X				X				X				
05 – Intraoperative Data Collection			X											
06 – Post Operative Assessments				X										
07 – Discharge Assessments					X									
08 – Leg Incision Pain Questionnaire					X									
09 – Leg Incision Pain 6 week						X								
10 – Leg Incision Assessment					X*	X*								
11 – Mace Event (6 week)						X								
12 – Phone Call Follow-up							X	X	X	X	X	X	X	
13 – MACE Event Form													X	
14 – Termination														X
15 – SAE														X
16 – SAE Follow-up														X
17 – Harvester Experience														X
18 – Protocol Noncompliance														X

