MACE, the composite endpoint that includes Death (all cause), Myocardial Infarction (MI) and Revascularization for myocardial ischemia, will be the primary outcome measure after randomization and the index CABG. Each randomized subject (either in Endoscopic or in Open harvesting group) will be followed after the index CABG to capture the time-to-MACE event where an ‘EVENT’ will be defined as either death (all cause) or an MI or a revascularization procedure during the follow-up period. Total follow-up period will be 6.5 years of which the first 4.5 years will be active follow-up (using in-clinic visit or by telephone) period and will be carried out by the site personnel. The remaining 2 years will be passive follow-up which will be carried out centrally by the chair’s office staff using the VA patient database. A minimum of 1 year of active follow-up will be used for subjects who will be randomized at the tail end of the 3-year projected enrollment period of the study. The subjects

who will either be lost to follow-up or will not experience an 'EVENT' before the end of the follow-up period will be considered as right censored.

The primary analysis of such time-to-Mace event data will include the events only from the active follow-up period (which is 4.5 years). The secondary analysis will include events from the entire 6.5 years of follow-up period.

Survival analysis techniques will be used to analyze the time-to-MACE event data for both primary and secondary analyses.

Kaplan-Meier analysis, a nonparametric method, will be used to estimate the survival (not experiencing MACE) over time in the two harvesting groups and a log-rank statistic will be used to test the equality of the survival function estimates in the two groups (the null hypothesis).

Cox's Proportional Hazards models will be used to investigate the effect of harvesting technique on the time until MACE adjusted for other potential influential variables, such as, age, gender, harvester's experience etc.

3. Secondary Outcomes Measures

One and Three-year MACE: This composite endpoint consists of

- i. Death (all cause);
- ii. Myocardial Infarction and
- iii. Revascularization for myocardial ischemia.

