--	--	--	--

5. Leg incision drainage (cc) (*if applicable*):

--	--	--	--

6. Leg incision dressings (*number of changes*):

--	--

7. Blood/Products Transfusion: No Yes 1. If yes, check all that apply: PRBCs FFP Platelets Cryoprecipitate8. Intra-aortic balloon pump: No Yes 9. ECMO: No Yes 10. Ventricular Assist Device: No Yes

--	--	--

--	--	--	--

--	--	--	--

11. POST-OP DAY #2.....

--	--

--	--

--	--	--	--

 month day year

12. ECG evidence of new pathologic Q waves or new LBBB: No Yes

If yes, obtain Cardiac Biomarkers of choice every 8 hours until downward trend is seen in level and
complete A, B, OR C below.

A. Peak Cardiac Troponin I

1. Peak Cardiac Troponin I (ng/mL):

--	--

 .

--	--

2. Reference Range (ng/mL)

--	--

 .

--	--

 to

--	--

 .

--	--

B. Peak Cardiac Troponin T

3. Peak Cardiac Troponin T (ng/mL):

--	--

 .

--	--

4. Reference Range (ng/mL)

--	--

 .

--	--

 to

--	--

 .

--	--

C. Peak CPK/MB Panel

7. Peak Total CPK (U/L):

--	--	--	--

8. Total CPK Reference Range (U/L)

--	--

 to

--	--	--	--

AND

9. Peak CK-MB (ng/mL):

--	--	--

 .

--

10. CK-MB Reference Range (ng/mL)

--

 to

--	--

 .

--

AND

11. Peak CK-MB Index (%):

--	--	--

 .

--

12. CK-MB Index Reference Range (%)

--	--

 .

--

 to

--	--

 .

--

13. ECG evidence of arrhythmia: No Yes

1. If yes, specify: atrial fibrillation
 atrial flutter
 pacemaker
 other, specify _____

14. Chest tube drainage (cc):

--	--	--	--

SITE NO.

--	--	--

SUBJECT ID

--	--	--	--

ALPHA CODE

--	--	--	--

15. Leg incision drainage (cc) (*if applicable*):

--	--	--	--

16. Leg incision dressings (*number of changes*):

--	--

17. Blood/Products Transfusion: No Yes

1. If yes, check all that apply:

- PRBCs
- FFP
- Platelets
- Cryoprecipitate

18. Intra-aortic balloon pump: No Yes

19. ECMO: No Yes

20. Ventricular Assist Device: No Yes

S.I. Signature _____ Date _____

SITE NO.

--	--	--

SUBJECT ID

--	--	--	--

ALPHA CODE

--	--	--	--

DATE FORM COMPLETED

--	--	--

Month Day Year

FORM 07 – DISCHARGE ASSESSMENT

1. Date of Discharge

--	--

 month

--	--

 day

--	--	--	--

 year2. Endotracheal tube extubation (final) > POD #2 No Yes →

--	--

 month

--	--

 day

--	--	--	--

 year3. Inotropic Agents > POD #2: No Yes

If yes, check all that apply:

- Dopamine
- Dobutamine
- Epinephrine
- Norepinephrine
- Amrinone
- Milrinone
- other, specify _____

4. Transfer order to step down (final) > POD #3 No Yes →

--	--

 month

--	--

 day

--	--	--	--

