SITE NO. 

 	 	 	

				SUBJECT ID 

 	 	 	 	

					ALPHA CODE 

 	 	 	 	

					DATE OF VISIT 

 	 	

 Month			

 	 	

 Day			

 	 	 	 	

 Year				

FORM 11 – 6 WEEK MACE EVENT FORM

1. Has the subject died after the last contact? No Yes
(If yes, complete Forms 14 and 15)

a. Date of death

--	--

Month

--	--

Day

--	--	--	--

Year

2. Did the subject have an acute myocardial infarction since the last contact? No Yes
(If yes, complete form 15 and 19)

a. AMI Date

--	--

Month

--	--

Day

--	--	--	--

Year

3. Did the subject receive PCI since the last contact? No Yes
If yes,

a. Procedure Date

--	--

Month

--	--

Day

--	--	--	--

Year

4. Did the subject receive CABG since the last contact? No Yes
If yes,

a. Procedure Date

--	--

Month

--	--

Day

--	--	--	--

Year

For Q 1-4 answered yes, obtain appropriate medical records for required source documentation.

--	--	--

--	--	--	--

--	--	--	--

MEDICATIONS

5. Has the subject taken any of the following medications in since last contact?

a. Beta blocker	No 	Yes 
b. ACE/ARB Inhibitor	No 	Yes 
c. Statin	No 	Yes 
d. Non-Statin LLA	No 	Yes 
e. Nitrate	No 	Yes 
f. Calcium Channel Blocker	No 	Yes 
g. Aspirin	No 	Yes 
h. Plavix	No 	Yes 
i. Warfarin	No 	Yes 

Form Completed By _____ Date _____

VISIT (Months)

--	--

SITE NO.

--	--	--

SUBJECT ID

--	--	--	--	--

ALPHA CODE

--	--	--	--	--

FORM 12 – PHONE CALL FOLLOW-UP FORM

1. Date of phone call (*or medical chart review*)

--	--

--	--

--	--	--	--	--

Month Day Year

2. Subject contacted successfully? No Yes

3. Did the subject die since the last contact? No Yes
If yes, (complete Forms 14 and 15)
a. Date of death

--	--

--	--

--	--	--	--	--

Month Day Year

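### No scheduled form shown asks about PCI or repeat CABG between the index CABG and discharge, or about in-hospital MI after post-operative day 2, and the look-back on Form 11 is undefined

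*Protocol*

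**What the plan says.** **Endpoint clock.** Protocol Section XVII.D.2 says each randomized subject "will be followed after the index CABG to capture the time-to-MACE event". SAP Section 7.1 likewise measures time from the index surgery date. MI and revascularization during the index stay are therefore primary-endpoint events.

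**Forms (Protocol Appendix E).** Form 06 asks, for post-operative days 1 and 2, about "ECG evidence of new pathologic Q waves or new LBBB", with biomarkers if the answer is yes. Next comes "FORM 07 – DISCHARGE ASSESSMENT". Form 11 at six weeks asks "Did the subject have an acute myocardial infarction since the last contact" and, for revascularization, "Did the subject receive PCI since the last contact", with a parallel item for CABG.

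**Assessment text (Protocol Section IX.C).** If the subject reports a MACE "after discharge from the hospital, then records will be obtained for final adjudication". On early morbidity it promises: "The presence/absence of major post-operative complications that occurred prior to discharge or within 30 days of CABG will be recorded".

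**SAE route.** Protocol Section X.C starts SAE monitoring at consent and requires reporting within three business days, whatever the relationship to the intervention. Section XI.B names major adverse cardiac events among the SAEs to be collected through surgery and at discharge.

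**The concern.** A component of the primary endpoint should be asked about over its whole at-risk period, in the same way for every subject. Here the period from surgery to discharge appears to have no scheduled question on revascularization, and none on MI after day 2.

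This window matters to the trial's own question. Protocol Section I says: "Endothelial dysfunction enhances thrombogenicity and may lead to early thrombosis and accelerated SVG failure". Early graft failure could show itself as an MI or a revascularization before the patient leaves hospital.

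Capture that depends on a site starting a form can be incomplete. It may also be uneven, because the coordinator who makes the randomization call receives the assignment (Protocol Appendix D, Randomization). The promised 30-day record of complications raises the same question: which form holds it?

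**Working it through.** **Step 1. Follow the forms from surgery to six weeks** (Protocol Table 2 and Appendix E).

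| Form | When | MI item | PCI / repeat CABG item |
|---|---|---|---|
| 06 | Post-op days 1 and 2 | ECG sign, then biomarkers | None |
| 07 | Discharge or day 30 (Visit 01) | None | None |
| 11 | Six weeks (Visit 02) | Yes, since last contact | Yes, since last contact |
| 13 | Month 49 only | Page not shown | Page not shown |
| 15 | As needed | Non-fatal MI box | No box |
| 19 | As needed | Any MI date, beside the index CABG date | Not applicable |

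Form 07 has nine items: discharge date, late extubation, late inotropes, late step-down, discharge after 7 days, creatinine, potassium, white cell count and hematocrit.

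**Step 2. Interpret the last contact.** Visit 01 comes directly before Visit 02. If the last contact is Visit 01, surgery to discharge falls outside the question on Form 11. If it means the operation, the window is covered. The supplied text does not say which, and 16 sites may read it differently.

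**Step 3. Check the fallback for each component.**
- *Death:* covered by Forms 14 and 15 and by VA databases (Section IX.C). No gap.
- *MI:* Form 15 has a box, Form 19 has no time limit, and Appendix C defines MI both within and beyond 48 hours. A route exists, but the site must start it.
- *PCI or repeat CABG:* no box on Form 15. Forms 11 and 12 send a yes for MI to Forms 15 and 19 but give no such instruction for PCI or CABG. SAP Sections 6.7 and 8 tabulate SAEs by MedDRA term and do not say that they feed MACE.

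**Step 4. Check the 30-day morbidity record.** No form shown has a yes/no item for major complications. Parts are recorded: balloon pump (Form 05 item 50 and Form 06), ECMO, ventricular assist device and transfusion (Form 06), and creatinine (Forms 02 and 07).

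**Step 5. Show what a loss would do, by assumption.** The plan gives no in-hospital rate, so this is a sensitivity range and not an estimate. It uses the one-year comparison on which the sample size rests, not the log-rank test.

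First, reproduce the plan. With p1 = 0.095, p2 = 0.155 and mean 0.125:

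n = [1.960 × √(2 × 0.125 × 0.875) + 1.036 × √(0.095 × 0.905 + 0.155 × 0.845)]² / 0.06², which rounds up to 545 per group, as stated. Power at 545 is 85.1%. Expected one-year events are 545 × (0.095 + 0.155) = 136.

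Now suppose a share f of one-year MACE is missed equally in both arms, so each rate is multiplied by (1 − f):

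| f | OVH vs EVH | Events missed | Power at 545 per group |
|---|---|---|---|
| 5% | 9.03% vs 14.73% | 7 | 83.0% |
| 10% | 8.55% vs 13.95% | 14 | 80.6% |
| 20% | 7.60% vs 12.40% | 27 | 75.3% |

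Each row gives no credit to Form 15, Form 19 or chart capture. It also ignores subjects who would be counted later through a second event.

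**The case against.** The strongest reply is that the index stay is under mandatory surveillance. SAE reporting starts at consent, and Section XI.B names MACE. A PCI or redo operation in hospital would ordinarily meet an SAE criterion, such as prolonged hospitalization or a need for surgical intervention. The leg-incision form also sends any stay beyond 14 days to Form 15. Section XV.A has the Clinical Events Committee confirm all reported MIs, with no discharge limit. The Section IX.C sentence concerns events that the subject reports, and the six-week text in Section X.A has no last-contact limit. Appendix D calls the forms drafts, the operations manual is not supplied, and Form 13 cannot be inspected. The index stay is also in a VA chart.

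Most of this stands, and it limits the point. A reader might infer that no form of any kind covers early MI, or that early MACE will be lost. The documents do not support either inference: Forms 15 and 19 provide a route for MI, and a reportable in-hospital PCI could appear as free text on Form 15.

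A reader might also infer that missed events fall mainly in the EVH arm and pull the result toward no difference. That needs arm-specific in-hospital rates, which are not given. Section II reports no significant EVH–OVH difference in the short-term composite in the earlier VA trial. Nor can it be said that perioperative safety goes unrecorded, since mechanical support, transfusion and creatinine are partly captured and SAP Table 23 gives SAEs by arm.

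The reply does not remove the gap for revascularization. The SAE route never asks about PCI or CABG by name, and the SAP does not link it to MACE. During active follow-up, the plan turns to VA records when a subject cannot be reached or may drop out (Section X.E, Section XVII.G, SAP Section 5.3). It does not do so for one who attends at six weeks and truthfully answers no for the time since discharge.

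**Conclusion.** The point holds for scheduled forms. On the forms shown, in-hospital PCI and repeat CABG have no scheduled question if the last contact is read as Visit 01. In-hospital MI after day 2 has none either, but has better fallbacks. Death is unaffected. The promised 30-day presence or absence of major complications has no yes/no item, though some components are recorded.

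The conclusion rests on three things: the ordinary reading of Visit 01 as the last contact, the forms as supplied, and no reliance on Form 13 in either direction. Neither the number of events missed nor the direction of any bias can be derived. The power figures only show sensitivity to an assumed equal loss. This is a should-fix matter: it concerns a component of the primary endpoint, but mandatory SAE reporting covers part of the window.

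**What to change.** - **Form 11:** make items 1 to 4 look back to the index CABG.
- **Form 07:** add dated yes/no items for MI, PCI and repeat CABG before discharge, and a yes/no item for the major complications promised in Section IX.C. For a subject discharged before day 30, carry the complication item onto Form 11 for the remaining days.
- **Section IX.C:** make record retrieval apply to MI and revascularization at any time after the index CABG.
- **Form 13:** it would also help to state when this form is completed.

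The cost is a few more tick-boxes, revision of two forms and one protocol sentence, and some chart back-entry for subjects already enrolled.
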